Molybdenum cofactor deficiency	10069687
Multiple subpial transection	10079825
Myoclonic epilepsy	10054859
Myoclonic epilepsy and ragged-red fibres	10069825
Partial seizures	10061334

PT	PT Code
Partial seizures with secondary generalisation	10056209
Petit mal epilepsy	10034759
Polymicrogyria	10073489
Post stroke epilepsy	10076982
Post stroke seizure	10076981
Postictal headache	10052470
Postictal paralysis	10052469
Postictal psychosis	10070669
Postictal state	10048727
Post-traumatic epilepsy	10036312
Schizencephaly	10073487
Seizure	10039906
Seizure anoxic	10039907
Seizure cluster	10071350
Seizure like phenomena	10071048
Severe myoclonic epilepsy of infancy	10073677
Simple partial seizures	10040703
Status epilepticus	10041962
Sudden unexplained death in epilepsy	10063894
Temporal lobe epilepsy	10043209
Tonic clonic movements	10051171
Tonic convulsion	10043994
Tonic posturing	10075125
Topectomy	10073488
Transient epileptic amnesia	10081728
Tuberous sclerosis complex	10080584
Uncinate fits	10045476

PTs (Selective)

PT	PT Code
Confusional state	10010305
Loss of consciousness	10024855
Syncope	10042772
Sopor	10058709
Stupor	10042264
Altered state of consciousness	10050093
Depressed level of consciousness	10012373
Consciousness fluctuating	10050093

14. Weight Gain**HLT General nutritional disorders NEC (Selective)**

PT	PT Code
Abdominal fat apron	10077983
Overweight	10033307
Abnormal weight gain	10000188
Central obesity	10065941
Obesity	10029883

HLT Physical examination procedures and organ system status (Selective)

PT	PT Code
Weight abnormal	10056814
Weight increased	10047899
Waist circumference increased	10064863
Body mass index abnormal	10074506
Body mass index increased	10005897

General signs and symptoms NEC (Selective)

PT	PT Code
Fat tissue increased	10016251

15. Rhabdomyolysis**Rhabdomyolysis/myopathy (SMQ)**

PT	PT Code
Muscle necrosis	10028320
Myoglobin blood increased	10028625
Myoglobin blood present	10059888
Myoglobin urine present	10028631
Myoglobinaemia	10058735
Myoglobinuria	10028629
Myopathy	10028641
Myopathy toxic	10028648
Necrotising myositis	10074769

PT	PT Code
Rhabdomyolysis	10039020
Thyrotoxic myopathy	10081524

PTs (Selective)

PT	PT Code
Myalgia	10028411
Myositis	10028653

16. Pancreatitis**Acute pancreatitis (SMQ)**

PT	PT Code
Cullen's sign	10059029
Grey Turner's sign	10075426
Haemorrhagic necrotic pancreatitis	10076058
Hereditary pancreatitis	10056976
Ischaemic pancreatitis	10066127
Oedematous pancreatitis	10052400
Pancreatic abscess	10048984
Pancreatic haemorrhage	10033625
Pancreatic necrosis	10058096
Pancreatic phlegmon	10056975
Pancreatic pseudoaneurysm	10081762
Pancreatic pseudocyst	10033635
Pancreatic pseudocyst drainage	10033636
Pancreatitis	10033645
Pancreatitis acute	10033647
Pancreatitis haemorrhagic	10033650
Pancreatitis necrotising	10033654
Pancreatitis relapsing	10033657
Pancreatorenal syndrome	10056277

17. Impact on Creatinine**Acute renal failure (SMQ)**

PT	PT Code
Acute kidney injury	10069339
Acute phosphate nephropathy	10069688

PT	PT Code
Anuria	10002847
Azotaemia	10003885
Continuous haemodiafiltration	10066338
Dialysis	10061105
Foetal renal impairment	10078987
Haemodialysis	10018875
Haemofiltration	10053090
Hyponatriuria	10077515
Neonatal anuria	10049778
Nephropathy toxic	10029155
Oliguria	10030302
Peritoneal dialysis	10034660
Prerenal failure	10072370
Renal failure	10038435
Renal failure neonatal	10038447
Renal impairment	10062237
Renal impairment neonatal	10049776

Renal Failure and Impairment HLT

PT	PT Code
Acute Kidney injury	10069339
Anuria	10002847
Atypical haemolytic uraemic syndrome	10079840
Cardiorenal syndrome	10068230
Chronic kidney disease	10064848
Crush syndrome	10050702
Diabetic end stage renal disease	10012660
End stage renal disease	10077512
Foetal renal impairment	10078987
Haemolytic uraemic syndrome	10018932
Hepatorenal failure	10019845
Hepatorenal syndrome	10019846
Nail-patella syndrome	10063431
Neonatal anuria	10049778
Oliguria	10030302
Pancreatorenal syndrome	10056277
Postoperative renal failure	10056675
Postrenal failure	10059345
Prerenal failure	10072370

PT	PT Code
Propofol infusion syndrome	10063181
Renal failure	10038435
Renal failure neonatal	10038447
Renal impairment	10062237
Renal impairment neonatal	10049776
Renal injury	10061481
Scleroderma renal crisis	10062553
Traumatic anuria	10044501

18. Safety in Pregnancy

Use AE terms co-reported in pregnancy exposures to CAB and/or RPV.

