8.2. Adverse Events of Special Interest Analyses

Adverse events of special interest (AESI) are determined for CAB and/or RPV based on pre-clinical and clinical experience, along with information for the Integrase Inhibitor class of HIV medications and RPV safety profile. Table 4 shows the currently identified AESI, drug(s) of Interest and the reasons for inclusion. Changes to the MedDRA dictionary may occur between the start of the study and the time of reporting, and/or

emerging data from on-going studies may highlight additional adverse events of special interest, therefore the list of AESIs may change at the time of reporting.

A summary by system organ class and preferred term will be provided for each of AESI. The characteristics of event occurrences during the maintenance phase will be summarized for common AESI which have at least 20 participants in either treatment arm. For Depression, anxiety and suicidal ideation/behaviour AESI, a summary by system organ class, maximum DAVIDS toxicity grade and prior history of suicidal ideation will be provided. The details of the planned grouping and planned displays are provided in Section 15.11 and Appendix 14: List of Data Displays.

Table 4 Adverse Events of Special Interest

Adverse Events of Special Interest	Drug(s) of Interest	Reason for Inclusion
Hepatic Safety Profile: Assessment of Risk of hepatotoxicity	CAB+RPV	Clinical, Class, Regulatory Interest, More prevalent in HIV population
Hypersensitivity Reactions (HSR)	CAB	Class, Regulatory Interest, Occurs in HIV population
Rash	RPV	Class, Regulatory Interest, Occurs in HIV population
Prolongation of the Corrected QT Interval of the ECG in Supratherapeutic Doses	RPV	Non-clinical, Clinical, Regulatory Interest
Suicidal Ideation/Behaviour	CAB+RPV	Clinical, Class, Regulatory Interest, More prevalent in HIV population
Depression	CAB+RPV	Clinical, Class, Regulatory Interest, More prevalent in HIV population
Bipolar Disorder	CAB+RPV	Clinical, Class, Regulatory Interest, More prevalent in HIV population
Psychosis	CAB+RPV	Clinical, Class, Regulatory Interest, More prevalent in HIV population
Mood Disorders	CAB+RPV	Clinical, Class, Regulatory Interest
Anxiety	CAB+RPV	Clinical, Class, Regulatory Interest
Sleep Disorders	CAB+RPV	Clinical, Class, Regulatory Interest, More prevalent in HIV population
Injection Site Reactions (ISR) from Study Drug Injections [1]	CAB+RPV	Clinical

Adverse Events of Special Interest	Drug(s) of Interest	Reason for Inclusion

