Seizures and Seizure-like Events	CAB	Clinical, Regulatory Interest
Weight Gain	CAB	Clinical, Class
Rhabdomyolysis	CAB	Clinical, Class
Pancreatitis	CAB	Clinical, Therapeutic Area, More prevalent in HIV population
Impact on Creatinine	CAB+RPV	Regulatory Interest, Therapeutic Area, More prevalent in HIV population
Safety in Pregnancy	CAB	Regulatory Interest, Class
NOTE: [1] A separate analysis will be performed for ISRs from study drug injections as described in Section 8.1.1.		

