15.11. Appendix 11: Identification of Adverse Events of Special Interest

The adverse events of special interest are identified based on MedDRA coded values and/or AE data available in the study database. The system organ classes (SOCs), preferred terms (PTs) or codes, Standardised MedDRA Queries (SMQs), High Level Group Terms (HLGTs), and High Level Terms (HLT) below are from MedDRA 21.1. SMQs use narrow terms unless otherwise specified. In case there is a change to the version of MedDRA at time of reporting, the coded values based on the MedDRA version at the time of reporting will be used. The additional events may also be added based on the blinded review of AE data collected on study prior to the database freeze.

1. Hepatic Safety Profile: Assessment of risk of hepatotoxicity

Hepatic failure, fibrosis and cirrhosis and other liver damage-related conditions (SMQ)

PT	PT Code
Acquired hepatocerebral degeneration	10080860
Acute hepatic failure	10000804
Acute on chronic liver failure	10077305
Acute yellow liver atrophy	10070815
Ascites	10003445
Asterixis	10003547
Bacterascites	10068547
Biliary cirrhosis	10004659
Biliary fibrosis	10004664
Cholestatic liver injury	10067969
Chronic hepatic failure	10057573
Coma hepatic	10010075
Cryptogenic cirrhosis	10063075
Diabetic hepatopathy	10071265
Drug-induced liver injury	10072268
Duodenal varices	10051010
Gallbladder varices	10072319
Gastric variceal injection	10076237
Gastric variceal ligation	10076238
Gastric varices	10051012
Gastric varices haemorrhage	10057572
Hepatectomy	10061997
Hepatic atrophy	10019637
Hepatic calcification	10065274
Hepatic cirrhosis	10019641
Hepatic encephalopathy	10019660
Hepatic encephalopathy prophylaxis	10066599

PT	PT Code
Hepatic failure	10019663
Hepatic fibrosis	10019668
Hepatic hydrothorax	10067365
Hepatic infiltration eosinophilic	10064668
Hepatic lesion	10061998
Hepatic necrosis	10019692
Hepatic steato-fibrosis	10077215
Hepatic steatosis	10019708
Hepatitis fulminant	10019772
Hepatobiliary disease	10062000
Hepatocellular foamy cell syndrome	10053244
Hepatocellular injury	10019837
Hepatopulmonary syndrome	10052274
Hepatorenal failure	10019845
Hepatorenal syndrome	10019846
Hepatotoxicity	10019851
Intestinal varices	10071502
Intestinal varices haemorrhage	10078058
Liver and small intestine transplant	10052280
Liver dialysis	10076640
Liver disorder	10024670
Liver injury	10067125
Liver operation	10062040
Liver transplant	10024714
Lupoid hepatic cirrhosis	10025129

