Minimal hepatic encephalopathy	10076204
Mixed liver injury	10066758
Nodular regenerative hyperplasia	10051081
Non-alcoholic fatty liver	10029530
Non-alcoholic steatohepatitis	10053219
Non-cirrhotic portal hypertension	10077259
Oedema due to hepatic disease	10049631
Oesophageal varices haemorrhage	10030210
Peripancreatic varices	10073215
Portal fibrosis	10074726
Portal hypertension	10036200
Portal hypertensive colopathy	10079446
Portal hypertensive enteropathy	10068923
Portal hypertensive gastropathy	10050897

PT	PT Code
Portal vein cavernous transformation	10073979
Portal vein dilatation	10073209
Portopulmonary hypertension	10067281
Primary biliary cholangitis	10080429
Regenerative siderotic hepatic nodule	10080679
Renal and liver transplant	10052279
Retrograde portal vein flow	10067338
Reye's syndrome	10039012
Reynold's syndrome	10070953
Splenic varices	10067823
Splenic varices haemorrhage	10068662
Steatohepatitis	10076331
Subacute hepatic failure	10056956
Varices oesophageal	10056091
Varicose veins of abdominal wall	10072284
White nipple sign	10078438

Hepatitis, non-infectious (SMQ)

PT	PT Code
Acute graft versus host disease in liver	10066263
Allergic hepatitis	10071198
Alloimmune hepatitis	10080576
Autoimmune hepatitis	10003827
Chronic graft versus host disease in liver	10072160
Chronic hepatitis	10008909
Graft versus host disease in liver	10064676
Hepatitis	10019717
Hepatitis acute	10019727
Hepatitis cholestatic	10019754
Hepatitis chronic active	10019755
Hepatitis chronic persistent	10019759
Hepatitis fulminant	10019772
Hepatitis toxic	10019795
Immune-mediated hepatitis	10078962
Ischaemic hepatitis	10023025
Lupus hepatitis	10067737
Non-alcoholic steatohepatitis	10053219
Radiation hepatitis	10051015
Steatohepatitis	10076331

2. Hypersensitivity Reactions (HSR)

Drug reaction with eosinophilia and systemic symptoms syndrome (SMQ)

PT	PT Code
Drug reaction with eosinophilia and systemic symptoms	10073508
Pseudolymphoma	10037127

PTs (Selective)

PT	PT Code
Drug hypersensitivity	10013700
Hypersensitivity	10020751
Type IV Hypersensitivity reaction	10053613
Eosinophilia	10014950
Eye swelling	10015967
Eyelid oedema	10015993
Lip swelling	10024570
Angioedema	10002424
Circumoral oedema	10052250
Face oedema	10016029
Idiopathic angioedema	10073257
Lip oedema	10024558
Mouth swelling	10075203
Oedema mouth	10030110
Periorbital oedema	10034545
Swelling face	10042682
Periorbital swelling	10056647
Swelling of eyelid	10042690

3. Rash

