3.66	3.71	NA	Safety	201585/primary_02/T3.100	Summary of Depression, Anxiety and Suicidal Ideation/Behaviour Adverse Events by System Organ Class, Maximum DAIDS Toxicity Grade, and Prior History of Depression, Anxiety and Suicidal Ideation at Screening (Maintenance Phase)		W48, W96
3.67-3.83	3.72-3.88	NA	Safety	209522/iss_01/T3.38-3.49, T3.51-3.55	Summary of XXX Adverse Events of Special Interest by System Organ Class and Preferred Term (Number of Subjects and Occurrence) – Maintenance Phase	Only display data from this study, no need for showing study number. For 'XXX', refer to Table 4 .	W48, W96
3.84	3.89	NA	Safety	209522/iss_01/T3.62	Summary of Characteristics of Common Adverse Events of Special Interest – Maintenance Phase	Only display data from this study, no need for showing study number. Present by individual common AESI.	W48, W96

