42	NA	NA	Oral Lead-in	201585/primary_02/L41	Listing of All Plasma HIV-1 RNA data for subjects with viral load ≥ 50 c/mL during the Maintenance Oral Lead-in Period	In column headers, replace 'Period' with 'Phase', replace 'Sample Day' with 'Study Day'.	W48
43	43	43	Intent-to-Treat Exposed	201585/primary_02/L43	Listing of HIV-1 Associated Conditions (Maintenance + Extension Phase)		W48, W96, EOS
Safety (list data during Maintenance and Extension Phases, unless otherwise specified)							
44	44	44	Safety	ABC_HSR_EX PO2	Listing of Abacavir Hypersensitivity Reaction Record - Exposure to Abacavir		W48, W96, EOS

Non-ICH Listings							
No. in W48	No. in W96	No. in EOS	Population	IDSL / Example Shell	Title	Programming Notes	Deliverable
45	45	45	Safety	ABC_HSR_DRUG2	Listing of Abacavir Hypersensitivity Reaction Record - Subject History of Drug Allergies		W48, W96, EOS
46	46	46	Safety	ABC_HSR_CO ND2	Listing of Abacavir Hypersensitivity Reaction Record - Subject and Family Conditions		W48, W96, EOS
47	47	47	Safety	ABC_HSR_RA SH2	Listing of Abacavir Hypersensitivity Reaction Record - Skin Rash Details		W48, W96, EOS
48	48	48	Safety	ABC_HSR_SY MP4	Listing of Abacavir Hypersensitivity Reaction Record - Symptoms		W48, W96, EOS
49	49	49	Safety	VS4	Listing of Abacavir Hypersensitivity Reaction Record - Vital Signs		W48, W96, EOS
50	50	50	Safety	ABC_HSR_SYMP6	Listing of Abacavir Hypersensitivity Reaction Record - Individual Symptoms and Diagnostic Category Assignments (Excluding Other Symptoms)		W48, W96, EOS
51	51	51	Safety	ABC_HSR_SY MP7	Listing of Abacavir Hypersensitivity Reaction Record - Individual Symptoms and Diagnostic Category Assignments (Other Symptoms)		W48, W96, EOS
52	52	52	Safety	201585/primary_02/L52	Listing of Liver monitoring/stopping Event Reporting		W48, W96, EOS
53	53	53	Safety	201585/primary_02/L53	Listing of Liver Event Information for RUCAM Score		W48, W96, EOS
54	54	54	Safety	201585/primary_02/L54	Listing of Liver Biopsy Details		W48, W96, EOS
55	55	55	Safety	201585/primary_02/L55	Listing of Liver Imaging Details		W48, W96, EOS

Non-ICH Listings							
No. in W48	No. in W96	No. in EOS	Population	IDSL / Example Shell	Title	Programming Notes	Deliverable
56	56	56	Safety	201585/primary_02/L59	Listing of Subjects Meeting Hepatobiliary Lab Criteria (Maintenance + Extension Phase)		W48, W96, EOS

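### The 20 terms that define the hypersensitivity AESI include no anaphylaxis or Type I term, so an event coded only that way is left out of the HSR table by default

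*SAP*

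**What the plan says.** Section 8.2 names hypersensitivity reactions as an AESI for CAB (Table 4) and makes a commitment for every AESI: "A summary by system organ class and preferred term will be provided for each of AESI". It refers to Section 15.11 for the grouping of terms.

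Section 15.11, under "2. Hypersensitivity Reactions (HSR", gives that grouping as two blocks: the DRESS SMQ and a block of selected preferred terms. The introduction to the same section says that SMQs are taken in their narrow form. It also leaves room for additions: "The additional events may also be added based on the blinded review of AE data collected on study prior to the database freeze". Section 8.2 has a second clause of this kind: "therefore the list of AESIs may change at the time of reporting".

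The display list (Section 15.14.5.4) delivers the commitment as a run of tables titled "Adverse Events of Special Interest by System Organ Class and Preferred Term (Number of Subjects and Occurrence"), numbered 3.67-3.83 at Week 48 and 3.72-3.88 at Week 96. Their shells come from another reporting effort, "209522/iss_01/T3.38-3.49, T3.51-3.55". Injection site reactions are handled apart from these: "A separate analysis will be performed for ISRs from study drug injections as described in Section 8.1.1".

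**The concern.** The heading is unqualified, in Table 4 and in Section 15.11 alike. Nothing in the SAP confines this AESI to delayed reactions, and the list is not built as if it were: it counts angioedema and a swollen eyelid. It names Type IV hypersensitivity but not Type I, and it has no anaphylaxis term. As the rule stands, eyelid swelling enters the hypersensitivity table automatically, while an event coded only as anaphylaxis enters only if someone decides to add it.

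What is at stake is the table that a reader would open first to compare hypersensitivity between the Q8W and Q4W arms. It could show a count that leaves out events most readers would expect under that title.

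**Working it through.** There is no figure in the plan to reproduce. The check is a count of the printed terms and a comparison of the displays.

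**1. Terms in item 2 (Section 15.11).**
- DRESS SMQ block: DRESS itself and pseudolymphoma = 2.
- Selected block: generic hypersensitivity 2, Type IV hypersensitivity 1, eosinophilia 1, angioedema 2, facial, oral or periorbital swelling 12. Sum: 2 + 1 + 1 + 2 + 12 = 18.
- Total: 2 + 18 = 20 distinct terms. Anaphylaxis or Type I terms among them: 0.

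**2. Could the Rash AESI (item 3) catch the event instead?** It has 14 SMQ terms and 20 selected terms, 14 + 20 = 34, and none is an anaphylaxis or Type I term. It is in any case a separate AESI, with RPV as the drug of interest, and its selected terms count only at Grade 3 or higher. No other AESI list in Section 15.11 carries such a term.

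**3. Tables that report the HSR AESI.**
- Table 4 lists 18 AESIs. Without injection site reactions, 18 − 1 = 17.
- Week 48: 83 − 67 + 1 = 17 tables. Week 96: 88 − 72 + 1 = 17 tables.
- Source shells T3.38-3.49 and T3.51-3.55: 12 + 5 = 17.

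So HSR has one table at each of the two analyses, and both use the same 20 terms.

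**4. Could another AESI display fill the gap?** The characteristics table for common AESIs (3.84 at Week 48, 3.89 at Week 96) uses the same definitions and requires at least 20 participants in an arm. With about 510 per arm (SAP Section 1), that is 20/510 = 3.9%. The SAP gives no HSR rate, so assume 0.1% to 1% and take X ~ Binomial(510, p):

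| Assumed rate p | P(X ≥ 20) in one arm |
|---|---|
| 0.1% | 2.5 × 10⁻²⁵ |
| 0.5% | 3.7 × 10⁻¹² |
| 1% | 3.8 × 10⁻⁷ |

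Over that range the table would in practice not be produced for HSR. The eight hypersensitivity listings (44 to 51: 51 − 44 + 1 = 8) are abacavir records, for example "Listing of Abacavir Hypersensitivity Reaction Record - Symptoms", and are not by-arm summaries.

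**5. Where the event would still appear.** At Week 48 it would be in the all-event tables (3.5, 3.6), in the serious event table (3.16) if serious, in the withdrawal table (3.22) if it led to withdrawal or permanent discontinuation of study drug, and in Listing 19.

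**6. Do the SAP's own clauses add the term?** The blinded-review clause and the list-change clause both say that a change may be made; neither names a term or a criterion. The provision for a change of MedDRA version updates coded values within the groupings already named and does not add a grouping. Section 15.11 also says that AESIs may be identified from other adverse event data in the database, but the only items that use this are injection site reactions (item 12) and pregnancy (item 18).

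**The case against.** The best case for the plan has four parts.

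- **Nothing is contradicted.** Section 8.2 promises a table for the grouping in Section 15.11, item 2 supplies a grouping marked as selective, and a table follows. Choosing the terms is a clinical judgement. This is true as far as it goes. But a deliberately narrow scope would need to be stated, and the swelling and angioedema terms do not fit a delayed-only scope.
- **The plan already allows additions before database freeze.** It does, and the team may well use that route. The default remains omission. In an open-label study it is also cleaner to fix terms in advance than to add them once events are known.
- **Existing coverage is wide.** This stands. The generic, angioedema and swelling terms will catch many immediate reactions, and a participant with any listed term co-reported is counted. The gap is confined to events coded only to an unlisted term.
- **The point relies on MedDRA conventions that the SAP does not print.** The absence of the terms is visible on the page. That such events may be coded to separate preferred terms is an assumption, to be checked in the dictionary version in use.

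A reader might go further and infer that immediate hypersensitivity as a whole is excluded, or that anaphylaxis would go unreported. The documents support neither: the list includes terms for immediate reactions, and the general tables and listings retain every coded event.

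**Conclusion.** The point holds as a minor one. The HSR definition is a fixed list of 20 terms with 0 for anaphylaxis or Type I hypersensitivity, under a heading that does not limit its scope. A participant with an event coded only to such a term is omitted by default from one descriptive by-arm table at Week 48 and one at Week 96.

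This rests on two assumptions: that such events can be coded to preferred terms outside the list, and that no listed term is co-reported. The SAP gives no expected number; it is likely to be small. No hypothesis test and no efficacy result is affected.

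**What to change.** In Section 15.11 item 2, before database freeze, add the narrow anaphylactic reaction SMQ (or the individual terms for anaphylactic reaction, anaphylactic shock and anaphylactoid reaction) and Type I hypersensitivity. Check the names against the MedDRA version used for reporting. Footnote the HSR table at both analyses with the count on the present 20 terms.

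The cost is a few lines in a term list; adverse events are already collected and coded. The drawback is that the AESI shells are borrowed from another reporting effort, so the list may depart from an HSR definition shared with other studies. Because the table is by preferred term, the added terms show as their own rows, and the footnote preserves the comparison.

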Severe cutaneous adverse reactions (SMQ)

PT	PT Code
Acute generalised exanthematous pustulosis	10048799
Cutaneous vasculitis	10011686
Dermatitis bullous	10012441
Dermatitis exfoliative	10012455
Dermatitis exfoliative generalised	10012456
Drug reaction with eosinophilia and systemic symptoms	10073508

PT	PT Code
Epidermal necrosis	10059284
Erythema multiforme	10015218
Exfoliative rash	10064579
Oculomucocutaneous syndrome	10030081
Skin necrosis	10040893
Stevens-Johnson syndrome	10042033
Toxic epidermal necrolysis	10044223
Toxic skin eruption	10057970

PTs (Selective), Grade 3 and higher

PT	PT Code
Eyelid rash	10074620
Genital rash	10018175
Mucocutaneous rash	10056671
Nodular rash	10075807
Perineal rash	10075364
Rash	10037844
Rash erythematous	10037855
Rash generalised	10037858
Rash macular	10037867
Rash maculo-papular	10037868
Rash maculovesicular	10050004
Rash morbilliform	10037870
Rash papular	10037876
Rash rubelliform	10057984
Rash scarlatiniform	10037890
Rash vesicular	10037898
Rash pruritic	10037884
Rash follicular	10037857
Rash pustular	10037888
Drug eruption	10013687

4. Prolongation of the Corrected QT Interval of the ECG in Supratherapeutic Doses

Torsade de pointes/QT prolongation (SMQ)

PT	PT Code
Electrocardiogram QT interval abnormal	10063748

PT	PT Code
Electrocardiogram QT prolonged	10014387
Long QT syndrome	10024803
Long QT syndrome congenital	10057926
Torsade de pointes	10044066
Ventricular tachycardia	10047302

PTs (Selective)

PT	PT Code
Electrocardiogram repolarisation abnormality	10052464

5. Suicidal Ideation/Behaviour**Suicide/self-injury (SMQ)**

PT	PT Code
Assisted suicide	10079105
Columbia suicide severity rating scale abnormal	10075616
Completed suicide	10010144
Depression suicidal	10012397
Intentional overdose	10022523
Intentional self-injury	10022524
Poisoning deliberate	10036000
Self-injurious ideation	10051154
Suicidal behaviour	10065604
Suicidal ideation	10042458
Suicide attempt	10042464
Suicide threat	10077417
Suspected suicide attempt	10081704

6. Depression**Depression (excl suicide and self injury) (SMQ)**

PT	PT Code
Activation syndrome	10066817
Adjustment disorder with depressed mood	10001297
Adjustment disorder with mixed anxiety and depressed mood	10001299
Agitated depression	10001496
Anhedonia	10002511

PT	PT Code
Antidepressant therapy	10054976
Childhood depression	10068631
Decreased interest	10011971
Depressed mood	10012374
Depression	10012378
Depression postoperative	10012390
Depressive symptom	10054089

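### The adverse event of special interest named for creatinine is built from 36 renal terms, none of which is a creatinine, creatinine-clearance or GFR term

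*SAP*

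**What the plan says.** SAP Section 8.2, Table 4, lists Impact on Creatinine as an adverse event of special interest (AESI) for CAB+RPV. The stated reasons are "Regulatory Interest, Therapeutic Area, More prevalent in HIV population". The same section promises a display: "A summary by system organ class and preferred term will be provided for each of AESI". It also provides a table of event characteristics for any AESI with at least 20 participants in either arm.

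Section 15.14.5.4 implements this as Tables 3.67 to 3.83, whose titles are filled in from the AESI names in Table 4, and Table 3.84 for the common AESIs.

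The terms that count towards each AESI are fixed in Section 15.11. For item 17, "17. Impact on Creatinine", there are two lists: the acute renal failure SMQ and the "Renal Failure and Impairment HLT". The general rule for that appendix is "SMQs use narrow terms unless otherwise specified", and item 17 specifies nothing broader. It has no block of individually selected terms, unlike items 2, 3, 4, 13 and 15. On later changes, the appendix says: "The additional events may also be added based on the blinded review of AE data collected on study prior to the database freeze".

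**The concern.** The name of this AESI and its definition do not match. It is named for a laboratory analyte, but its term list covers renal failure, impairment and injury, dialysis and filtration procedures, anuria and oliguria, and a number of syndromes. An investigator who reports a rise in creatinine as an adverse event, coded to a creatinine or GFR term, contributes nothing to the table that carries that name.

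Two planned outputs are affected. One is the by-arm AESI summary: its title comes from Table 4, so few or no events in it could be read as absence of a creatinine signal. The other is the event-characteristics table. Leaving out the creatinine and GFR terms can only lower this AESI's count, which may decide whether it reaches the threshold of 20 participants in an arm.

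**Working it through.** No SAP figure has to be reproduced. The check is a count of the printed terms, followed by a comparison with the other AESIs named for a measurement.

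**Item 17 (Section 15.11)**

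- Acute renal failure SMQ: 19 terms printed.
- Renal failure and impairment HLT: 27 terms printed.
- In both lists: 10 terms (acute kidney injury; anuria; foetal renal impairment; neonatal anuria; oliguria; prerenal failure; renal failure; renal failure neonatal; renal impairment; renal impairment neonatal).
- Distinct terms: 19 + 27 − 10 = 36. Matching by preferred term code and by name (ignoring case) gives the same total.
- Distinct terms whose name contains creatinine, GFR, glomerular, filtration rate or clearance: 0 of 36.

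The nearest related term is azotaemia, which is not a creatinine term. Some entries, such as Nail-patella syndrome and Crush syndrome, are further still from a creatinine effect.

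**Other AESIs named for a measured quantity (same appendix)**

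| AESI | Terms printed | Measurement or finding terms |
|---|---|---|
| Item 4, QT prolongation | 6 (SMQ) + 1 (selected) = 7 | 3, for example "Electrocardiogram QT interval abnormal" |
| Item 14, weight gain | 5 + 5 + 1 = 11 | 5 (weight, waist circumference, BMI) |
| Item 17, creatinine | 36 distinct | 0 |

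Item 15 (rhabdomyolysis) points the same way: its printed list includes a raised blood myoglobin term and adds two individually selected terms. The appendix therefore uses finding-type terms elsewhere, and has a mechanism for adding terms outside an SMQ.

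**Where creatinine events and values remain visible**

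- Adverse events, term by term: the all-event tables (3.5, 3.6), the drug-related tables (3.12, 3.13), the withdrawal table (3.22) and the listing of all adverse events (Listing 19).
- Laboratory data: chemistry change from baseline and values by visit (3.39, 3.40, with GFR in both unit systems) and maximum emergent chemistry toxicities (3.43). Section 15.6.4 specifies GFR from creatinine and from cystatin C.

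None of these is a grouped creatinine AESI display.

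**The case against.** The strongest counter-argument is that the appendix follows a coherent convention: AESI lists collect clinical conditions, and laboratory change belongs in the laboratory tables. Item 1 (hepatotoxicity) prints no ALT, AST or bilirubin term, and item 16 (pancreatitis) prints no lipase or amylase term. On that view item 17 is a renal-event list under a loose heading, and renaming it would be enough. This stands only in part. Items 1 and 16 are named for organ conditions and their lists match their names. Item 17 is named for the analyte, which puts it with QT and weight, whose lists do include measurement terms.

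It can also be said that measured and graded creatinine and GFR describe a creatinine effect better than reported adverse events do, and that the events themselves are not lost. Both points stand and limit the consequence. They do not supply the grouped summary that Section 8.2 promises for each AESI.

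The risk of misreading is reduced because the AESI table prints every contributing preferred term, so a careful reader would see that there is no creatinine row. That also stands, but the title still states something the content cannot show.

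Finally, Section 8.2 and Appendix 11 both allow the lists to change before reporting. The wording is permissive and commits to nothing. A core term that can be foreseen now should not depend on a later discretionary step.

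**Conclusion.** The concern holds. As printed, 0 of the 36 distinct terms defining the creatinine AESI is a creatinine, creatinine-clearance or GFR term, so its summary cannot count adverse events of raised creatinine or reduced GFR. This follows from the printed lists and the narrow-SMQ rule, and assumes that no terms are added under the optional clause.

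The consequence is confined to one grouped safety display and possibly its entry in the event-characteristics table. No efficacy endpoint, hypothesis test or analysis population depends on it. The number of participants affected cannot be stated, because the SAP gives no rate of creatinine adverse events. The SAP also gives no reason for choosing these two groupings, so whether the omission was deliberate cannot be settled from the document. The correction is worth making because it changes what a pre-specified safety table reports and costs very little.

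**What to change.** Add to item 17 of Section 15.11 the investigation preferred terms for creatinine, creatinine clearance and GFR from the MedDRA version in use at reporting, as a block of selected terms like the one in item 4. In the AESI summary, show them as a sub-row separate from the renal failure and impairment terms, so that both can be read by arm. Make the change before database freeze.

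The cost is a term-list edit on adverse event data already collected and coded; no new data or change of method is needed. The downside is that the AESI total rises and includes milder, laboratory-only events. The separate sub-row limits that, because the more serious renal events stay visible on their own.
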